\*\*~~CCI~~ [REDACTED], ideally from the same site of disease (e.g. liver, lymph node etc) that the 'on treatment' biopsy will be taken from, and taken after completion of all prior standard of care treatments will be accepted as a baseline biopsy.

- 8 Patients with adequate organ functions as described below;
  - AST/ALT  $\leq$  2.5X ULN (upper limit of normal) [with no underlying Liver Metastasis]
  - AST/ALT  $\leq$  5 X ULN [with underlying Liver Metastasis]
  - Total Bilirubin  $\leq$  1.5 X ULN
  - Serum Creatinine  $\leq$  1.5 X ULN
  - ANC  $\geq$  1.5  $\times$  10^9/L
  - Platelets  $>$  100  $\times$  10^9/L
  - Hb  $>$  8.5g/dL (with or without transfusional support)
  - Calculated creatinine clearance (CrCL)  $\geq$  60 mL/min as determined by Cockcroft Gault (using actual body weight).

Males:

$$\text{CrCL} = \frac{\text{Weight (kg)} \times (140 - \text{Age})}{72 \times \text{serum creatinine (mg/dL)}}$$

Females:

$$\text{CrCL} = \frac{\text{Weight (kg)} \times (140 - \text{Age})}{72 \times \text{serum creatinine (mg/dL)}} \times 0.85$$

- 9 Female patients of childbearing potential must have a negative pregnancy test prior to start of dosing
- 10 Female patients of childbearing potential and male patients with female partners of childbearing potential must agree to use a highly effective method of contraception during the study and for at least 5 months after the last dose of study drug. See Section 5.3.1 for details of acceptable methods of contraception

**For patients on RXC004 monotherapy treatment (Arm A) the following inclusion criteria will also apply to enter the RXC004 + nivolumab treatment phase;**

11. Patients must have had documented RECIST1.1 defined radiological progression on RXC004 monotherapy treatment on the first scheduled scan (week 8 +/- 1 week)
12. Patients must receive Cycle 1 Day 1 of combination study treatment within 28 days of the first scheduled scan (week 8 +/- 1 week) showing RECIST1.1 defined radiological progression, or for clinically stable patients that remain on RXC004 after RECIST1.1 defined radiological progression, within 28 days of the most recent scan showing further radiological progression or confirmation of the week 8 RECIST1.1 progression (see Section 7.1.1 and Appendix D for more details)

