## **6.6 Dose Modification**

RXC004 dose reduction and interruption are permitted. Nivolumab dose reduction is not permitted but dose interruption/delay is permitted as per Appendix G.

RXC004 may be dose interrupted (withheld) until a clinically significant (any grade) and/or a grade  $\geq 3$  related adverse event resolves to baseline or  $\leq$  grade 2. RXC004 may also be withheld if it is necessary to give a concomitant medication that is a moderate or strong CYP3A4 inhibitor. RXC004 related colitis events should be managed as per Appendix J.

Adverse events that are assessed as being causally related nivolumab should be managed as per the Nivolumab Toxicity Management and Dose Modification Guidelines (Appendix G). If either agent is interrupted or discontinued for a related-AE the other agent (nivolumab or RXC004) may be continued if the patient is judged (by the investigator) to be receiving clinical benefit.

RXC004 and nivolumab dose interruption and stopping criteria are detailed in Table 14.

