	Grade 3 or 4	
Admit patient and perform investigations as per Grade 2.
 
Treat with (methyl)prednisolone IV 2-4 mg/kg/day and cover with empiric antibiotics. Once improved to baseline wean steroids over at least 8 weeks. If no improvement after 48hrs add infliximab 5 mg/kg (or MMF if concurrent hepatic toxicity).
 
High resolution CT +/- bronchoscopy and BAL pending appearances
 
Permanently discontinue

Hepatitis	Grade 1: ALT or AST >ULN-3XULN	
If > ULN-3XULN repeat in 1 week
 
Continue treatment

	Grade 2: ALT or AST 3-5XULN	
Re-check LFTs/INR/albumin every 3 days. Review medications, e.g. statins, antibiotics and alcohol history. Perform liver screen: Hepatitis A/B/C serology, Hepatitis E PCR, anti-ANA/SMA/LKM/SLA/LP/LCI, iron studies
 
If rising ALT/AST when re-checked start oral prednisolone 1 mg/kg. Once resolved to Grade 1, wean steroids over 2 weeks. Re-escalate if worsening; nivolumab treatment may be resumed once prednisolone <math>\leq</math> 10 mg

Adverse Event	Severity	Investigations, Treatment and Dose modification
		
Consider imaging for metastases/clot
 
Withhold dosea
 
Grade 3:AST or ALT 5-20XULN
 
Re-check LFTs/INR/albumin every day. Other investigation as per Grade 2.
 
If ALT/AST < 400 and normal bilirubin/INR/albumin treat with oral prednisolone 1 mg/kg. If ALT/AST > 400 or raised bilirubin/INR/low albumin treat with i.v. (methyl)prednisolone 2 mg/kg. Once improved to G2, can change to oral prednisolone and wean over 4 weeks
 
Perform US with Doppler. Low threshold to admit if clinical concern
 
Permanently discontinue

	Grade 4: ALT or AST >20xULN	
Investigations as per Grade 3
 
Treat with i.v. (methyl)prednisolone 2 mg/kg. If condition worsens despite steroids, add mycophenolate mofetil (MMF) 500-1000 mg bd. If worse on MMF, consider addition of tacrolimus.
 
Hepatology consult and consider liver biopsy
 
Permanently discontinue

Hypophysitis	Grade 2	
Pituitary axis assessment, MRI pituitary protocol (also exclude brain metastases), visual field assessment. Monitor TFTs.
 
Start oral prednisolone 0.5-1 mg/kg od after pituitary axis assessment. If no improvement in 48h, treat as severe with i.v. (methyl)prednisolone. Wean steroids based on symptoms over 2-4 weeks to 5 mg prednisolone. Do not stop steroids
 
Refer to or consult endocrinologist
 
Withhold dosec

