Other	Other Grade 3AEs - First occurrence - Recurrence of same Grade 3 adverse events	
Withhold dosea
 
Permanently discontinue

	Life-threatening or Grade 4 adverse reaction	Permanently discontinue
	Grade 3 myocarditis	If myocarditis is suspected, admit the patient and immediately start high-dose (methyl)prednisolone (1-2 mg/kg). In the case of deterioration, consider

Adverse Event	Severity	Investigations, Treatment and Dose modification
		
adding another immunosuppressive drug (MMF or tacrolimus)
 
Permanently discontinue
 
Guillain-Barré syndrome (GBS)
 
Nerve conduction studies (acute polyneuropathy) Lumbar puncture (elevated protein with normal WBC count). Pulmonary function tests with vital capacity and maximum inspiratory/expiratory pressures. Antibody testing for GBS variants, e.g. GQ1b in Miller Fisher variant
 
Use of steroids not recommended in idiopathic GBS If no improvement or worsening, plasmapheresis or intravenous immunoglobulin indicated.
 
Neurological consult. Consider location of care where ventilatory support available (required in 15%-30% idiopathic cases)
 
Permanently discontinue

	Myasthenia Gravis	
Check for ocular muscle and proximal muscle fatigability. AChR and anti-MuSK antibodies Bedside tests, e.g. Tensilon test or ice pack test with neurological input. Repetitive nerve stimulation and single fibre EMG
 
Steroids indicated (oral or i.v. depending on symptoms). Pyridostigmine initial dose 30 mg tds. If no improvement or worsening, plasmapheresis or IVIG may be considered Additional immunosuppressants azathioprine, cyclosporine, mycophenolate Avoid certain medications, e.g. ciprofloxacin, beta-blockers, that may precipitate cholinergic crisis
 
Neurological consult
 
Permanently discontinue

	Requirement for 10 mg per day or greater prednisone or equivalent for more than 12 weeks	Permanently discontinue
	Persistent Grade 2 or 3 adverse event lasting 12 weeks or longer	Permanently discontinue

a Resume treatment when adverse reaction improves to Grade 0 or 1

b Other immunosuppressive treatment options – MMF 500-1000 mg bid or tacrolimus

c Withhold dose until symptoms resolve and any steroid treatment is complete. Treatment should be continued in the presence of hormone replacement therapy as long as no symptoms are present

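### Table 19 gives patients who enter with AST/ALT above 3 x ULN no return-to-baseline route back to nivolumab after a related rise, and the protocol is inconsistent on whether causality is required

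*Protocol*

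**What the plan says.** **Eligibility.** Protocol Section 5.1, criterion 8, applies to both arms. It caps AST/ALT at "2.5X ULN (upper limit of normal) [with no underlying Liver Metastasis" and, for the other group, at "5 X ULN [with underlying Liver Metastasis".

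**Nivolumab management.** The hepatitis rows of Table 19 use multiples of ULN only:
- "Grade 1: ALT or AST >ULN-3XULN": continue.
- "Grade 2: ALT or AST 3-5XULN": withhold.
- "Grade 3:AST or ALT 5-20XULN": permanently discontinue.
- "Grade 4: ALT or AST >20xULN": permanently discontinue.

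Footnote a, which governs the hold, reads "Resume treatment when adverse reaction improves to Grade 0 or 1". Table 14 likewise sets Grade 1 or lower as the condition for restarting nivolumab. A later row of Table 19 permanently stops nivolumab when a Grade 2 or 3 event persists for 12 weeks or more.

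**When Appendix G applies.** Section 6.6 says: "Adverse events that are assessed as being causally related nivolumab should be managed as per the Nivolumab Toxicity Management" and dose modification guidelines. Table 14's rows for a nivolumab hold and for nivolumab discontinuation cover any event that meets the Appendix G criteria, and do not mention causality. Section 7.1 stops study drug for an adverse event that meets the Appendix G or Table 14 discontinuation criteria, again without causality.

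**Laboratory values.** Section 8.3.5 frames laboratory adverse events as deterioration from baseline.

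**The concern.** Criterion 8 deliberately admits patients whose enzymes are already raised by liver metastases. The hepatitis rows then grade and manage them on a scale that ignores where they started. For a patient who entered above 3 x ULN, full recovery from a nivolumab-related rise still counts as Grade 2 on that scale.

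At stake is continued nivolumab for some eligible patients in Arm B and in the Arm A combination phase, and uniform handling across sites. A site that reads resolution as recovery to baseline would restart nivolumab. A site that reads the grade literally would not, and after 12 weeks might stop it for good. A further split is possible because Section 6.6 requires attribution to nivolumab while Table 14 and Section 7.1 do not say so.

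**Working it through.** No sample size or power figure is involved. The check sets the thresholds side by side and then follows a patient through the rules.

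**1. Overlap of the ranges (multiples of ULN)**

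| AST/ALT | Eligible, no liver metastasis | Eligible, liver metastasis | Table 19 hepatitis action |
|---|---|---|---|
| up to 3 | yes, to 2.5 | yes | continue |
| 3 to 5 | no | yes | withhold |
| 5 to 20 | no | only at exactly 5 | permanently discontinue |
| above 20 | no | no | permanently discontinue |

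Without liver metastasis, 2.5 is below 3 and there is no overlap. With liver metastasis, the entry range spans the whole withhold band. The value 5 appears in both the Grade 2 and the Grade 3 row.

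**2. Does the entry value trigger a hold?** No. Section 6.6 needs an adverse event attributed to nivolumab. An elevation present before the first nivolumab dose is not one, and an unchanged value is not a deterioration under Section 8.3.5.

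**3. What happens after a related rise?** Let b be the entry value in multiples of ULN, with b above 3 and up to 5. The entry values used below are illustrative.

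- Relative rise that reaches the permanent-stop band: 5/b - 1. For b = 4, 5/4 - 1 = 25%. For b = 4.5, 5/4.5 - 1 = 11%.
- Fall below the patient's own baseline needed to reach Grade 1 (3 x ULN or less): 1 - 3/b. For b = 4, 1 - 3/4 = 25%. For b = 4.5, 1 - 3/4.5 = 33%.

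So a patient who enters at 4 x ULN, is held for a related rise and recovers fully to 4 x ULN is still in the Grade 2 band. Neither footnote a nor Table 14's restart condition is met. If the value stays there, the 12-week persistence row can apply.

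**4. Is a baseline allowance given elsewhere?** Yes. The Grade 2 nephritis row of Table 19 accepts a return to Grade 1 or baseline, and allows treatment to continue if the event is not attributed to an immune-related cause. Table 14's rule for RXC004 after a first Grade 3 toxicity also accepts a return to baseline. The hepatitis rows contain neither allowance.

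**5. Is causality stated consistently?** No. Section 6.6 states it. Some Table 14 rows label the event as related to RXC004 or nivolumab. The two Table 14 rows that point to the Appendix G hold and discontinuation criteria do not, nor does Section 7.1.

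**The case against.** The strongest reply is that the protocol already deals with tumour-related elevations, though outside Table 19. Section 6.6 limits Appendix G to nivolumab-related events. Section 8.3.5 judges laboratory events against baseline and excludes deterioration that is clearly due to progression. Appendix B 3 lists the underlying disease among alternative causes. The schedule footnotes on nivolumab dosing allow an infusion to be held for an adverse event and set no enzyme threshold. The Grade 2 hepatitis row itself prompts imaging for metastases, and starts steroids only if enzymes rise on re-check. Appendix G also says that it summarises the nivolumab prescribing information, which is not among the documents and may contain baseline guidance.

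Most of this stands, and it defeats a stronger reading that the overlap invites: that eligible patients begin combination treatment already under a mandatory hold. It also means that crossing 5 x ULN through tumour growth is not, under Section 6.6, a reason to stop nivolumab.

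It does not settle what happens once a rise is attributed to nivolumab. One could argue from Section 8.3.5 that the event is over when the value is back at baseline. But footnote a and Table 14 express resumption as a grade, and Table 19 prints absolute bands for that grade. Nor does the reply explain why Table 14 and Section 7.1 leave out the causality condition.

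A reader might also infer a bias in Arm B's primary endpoint, since one patient among 20 evaluable is 5 percentage points of ORR. The documents do not support that. It would require the hold or stop to change a patient's response status, which nothing shows, and the share entering above 3 x ULN is not given.

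**Conclusion.** The point holds as an on-treatment inconsistency. It concerns patients with liver metastases who entered with AST/ALT above 3 x ULN, receive nivolumab in Arm B or the Arm A combination phase, and have a later rise judged nivolumab-related. For them, the written resume condition is not met by recovery to their own baseline, and the 12-week persistence stop can follow. Those who entered just below 5 x ULN reach the permanent-stop band after a small rise. Separately, Section 6.6 differs from Table 14 and Section 7.1 on whether causality is required.

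The per-patient sizes in the working depend on the entry values chosen. The number of patients affected cannot be derived from the documents, and no size of effect on ORR is claimed. The conclusion assumes that Table 19's printed bands define the grades named in footnote a and in the persistence row.

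**What to change.** Reconcile inclusion criterion 8, Section 6.6, the nivolumab hold and discontinuation rows of Table 14, Section 7.1, and the Table 19 hepatitis rows with footnote a and the 12-week persistence row. The text should state consistently:

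- whether attribution to nivolumab is required before the Appendix G hold and stop criteria apply;
- how an AST/ALT value already raised at baseline is treated for hold, for resumption and for permanent discontinuation;
- which row governs a value of exactly 5 x ULN;
- for Arm A patients who move to the combination, which assessment counts as baseline, since protocol Section 9.4.1 defines it before the first dose of study treatment and not before the first nivolumab dose.

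Which rule or threshold applies is for the sponsor's clinicians. The cost is a protocol clarification, with no additional data or patients.

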	Grade 3	
Investigations as per Grade 2
 
Initiate i.v. (methyl)prednisolone 1 mg/kg after sending bloods for pituitary axis assessment.
 
Analgesia as needed for headache. Aim convert to prednisolone and wean as symptoms allow over 4 weeks to 5 mg

Adverse Event	Severity	Investigations, Treatment and Dose modification
		Refer to or consult endocrinologist  Withhold dose c
	Grade 4	Investigations as per Grade 1  Treatment as per Grade 3  Refer to or consult endocrinologist  Permanently discontinue
Adrenal Insufficiency	Grade 2	Consider management with corticosteroids (if needed for symptoms of acute inflammation)  Withhold dose c
	Grade 3 or 4	Permanently discontinue
Type 1 Diabetes Mellitus	Grade 3 hyperglycaemia/diabetes	Admit to hospital immediately and start treatment of newly onset type I DM.  Consider management with corticosteroids (if needed for symptoms of acute inflammation)  Withhold dose c
	Grade 4 hyperglycaemia/diabetes	Treat as per Grade 3  Permanently discontinue
Nephritis and Renal Dysfunction	Grade 1 (creatinine 1.5 x baseline or > ULN-1.5x ULN)	Review hydration status, medications, urine test/culture if urinary tract infection symptoms Dipstick urine and send for protein assessment UPCR. Repeat creatinine weekly. If worsens, manage as per Grade 2  If obstruction suspected: renal ultrasound +/- doppler to exclude obstruction/clot  Continue treatment
	Grade 2: creatinine > 1.5-3x baseline or > 1.5-3x ULN	Investigation as per Grade 1 and review creatinine/K+ in 48h-72h; if not improving discuss with nephrologist and need for biopsy and if attributed to irAE, If proteinuria: for 24 h collection or UPCR If blood: phase contrast microscopy and GN screen* if nephrologist recommends  Initiate steroids (oral prednisolone 0.5-1 mg/kg)

Adverse Event	Severity	Investigations, Treatment and Dose modification
		
Renal ultrasound +/- doppler to exclude obstruction/clot
 
Withhold dosea - Repeat creatinine/K+ every 48h If returns to G1/baseline – recommence treatment (if on steroids, only once < 10 mg prednisolone) If not attributed to irAE - may continue treatment

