	Grade 3: creatinine > 3x baseline or > 3-6x ULN Serum creatinine more than 1.5 and up to 6 times the ULN	
Investigation as per Grade 2, plus admit patient for monitoring and fluid balance; repeat creatinine every 24h; early discussion with nephrologist and need for biopsy; if worsening, initiate i.v. (methyl)prednisolone 1-2 mg/kg
 
Withhold dosea

	Serum creatinine >6 x ULN	
Investigations as per G3, plus patient should be managed in hospital where renal replacement therapy is available
 
initiate i.v. (methyl)prednisolone 1-2 mg/kg
 
Permanently discontinue

Skin	Grade 1 (skin rash with or without symptoms, <10% BSA)	
Physical examination. Exclude other causes e.g. viral illness, infection, other drug rash etc
 
Topical steroids (mild strength) +/- oral or topical anti-histamines may be administered
 
Continue treatment

	Grade 2 (10-30% BSA)	
Investigations as per Grade 1
 
Topical steroids (moderate strength) +/- oral or topical anti-histamines may be administered
 
Consider dermatology referral and skin biopsy
 
Continue treatment

	Grade 3 rash (>30% BSA, or 10-30% BSA with substantial symptoms) or suspected Stevens-Johnson syndrome (SJS) or toxic epidermal necrolysis (TEN)	
Investigations as per Grade 1
 
Topical treatments as above (potent). Initiate steroids: if mild to moderate 0.5-1 mg/kg prednisolone od for 3 days then wean over 1-2 weeks; or if severe i.v. (methyl)prednisolone 0.5-1 mg/kg and convert to oral steroids on response, wean over 2-4 weeks
 
Dermatology referral and skin biopsy

Adverse Event	Severity	Investigations, Treatment and Dose modification
		Withhold dose a
	Grade 4 rash or confirmed SJS or TEN	Investigations as per Grade 1 i.v. (methyl)prednisolone 1-2 mg/kg Seek urgent dermatology review Permanently discontinue
Peripheral neurological toxicity (For specific recommendations for Myasthenia Gravis and Guillain-Barré syndrome, see 'other')	Grade 1	Comprehensive neurological examination Diabetic screen, B12/folate, HIV, TSH, consider vasculitic & autoimmune screen, review alcohol history & other medications Consider need for MRI/MRA brain or spine (exclude CVA, structural cause) Continue treatment

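### In Table 19 the Grade 3 nephritis cell carries a second creatinine range that takes in the whole Grade 2 ULN band, so one value can call for two different managements

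*Protocol*

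**What the plan says.** The Nephritis and Renal Dysfunction block of Table 19 defines four levels. Grade 1 runs up to 1.5x ULN. The next label is "Grade 2: creatinine > 1.5-3x baseline or > 1.5-3x ULN". The third cell carries two statements: the label "Grade 3: creatinine > 3x baseline or > 3-6x ULN", and then "Serum creatinine more than 1.5 and up to 6 times the ULN". The top level, which has no grade number, is "Serum creatinine >6 x ULN" and leads to permanent discontinuation.

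The Grade 2 row asks the site to "review creatinine/K+ in 48h-72h; if not improving discuss with nephrologist", to start oral prednisolone, and to withhold nivolumab with the instruction "Repeat creatinine/K+ every 48h". It adds that treatment may go on if the rise is not put down to an immune-related event. The Grade 3 row builds on the Grade 2 investigations and adds "admit patient for monitoring and fluid balance; repeat creatinine every 24h; early discussion with nephrologist", with intravenous steroid if creatinine worsens. It withholds nivolumab and has no continuation clause.

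Section 6.6 directs nivolumab-related events to Appendix G, and the nivolumab hold row of Table 14 points there as well.

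**The concern.** A severity cell should give one range. This one gives two that disagree, and the wider one reaches down over all of Grade 2. Neither a footnote to Table 19 nor the text of Section 6.6 reconciles them.

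This is an operative dose-modification table. Two combination patients with the same creatinine could be admitted or not, and be checked daily or every second day. If the rise is not thought immune-related, nivolumab could be stopped in one and continued in the other. That last case is within reach because the Table 14 hold row covers any event meeting a nivolumab hold, not only events already attributed to nivolumab. A site cannot tell which course complies with the protocol.

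**Working it through.** **1. The bands on the ULN scale** (Table 19)

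| Entry | Relative to baseline | Relative to ULN |
|---|---|---|
| Grade 1 | 1.5x | >1 to 1.5 |
| Grade 2 | >1.5 to 3x | >1.5 to 3 |
| Grade 3, label | >3x | >3 to 6 |
| Grade 3, added line | none | >1.5 to 6 |
| Top level | none | >6 |

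The labelled Grade 2 and Grade 3 bands do not overlap, and there is no gap between them. The added line overlaps Grade 2 over all of (1.5, 3], which is 1.5/4.5 = one third of the added line's own width.

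**2. A worked patient.** Creatinine 2x ULN, baseline 0.8x ULN: 2/0.8 = 2.5x baseline. The patient is Grade 2 on both labelled criteria, is not Grade 3 on either, but falls inside the added line. At 2x ULN a patient is already Grade 3 through the baseline criterion only if baseline is below 2/3 = 0.67x ULN, so the conflict at this value is clean from about 0.67x upward.

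**3. What the two rows then require**

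| | Grade 2 row | Grade 3 row |
|---|---|---|
| Admission | not called for | required |
| Creatinine | at 48–72 h, then every 48 h | every 24 h |
| Nephrologist | if not improving | early |
| Steroid | oral, 0.5–1 mg/kg, started | i.v., 1–2 mg/kg, if worsening |
| Nivolumab | withhold; may continue if not immune-related | withhold |

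Checks in the first 168 hours: every 24 h gives 168/24 = 7. A first check at 48 h and then every 48 h gives 3 (48, 96, 144 h). A first check at 72 h also gives 3 (72, 120, 168 h).

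**4. How much of the Grade 2 band is affected.** Let b be baseline creatinine as a multiple of ULN. Values above 3b are Grade 3 anyway, so the added line alone moves creatinine in (1.5, min(3, 3b)] x ULN. The share of the Grade 2 ULN band is (min(3, 3b) − 1.5)/1.5.

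| b | Values moved (x ULN) | Share |
|---|---|---|
| ≤0.5 | none | 0% |
| 0.6 | 1.5–1.8 | 20% |
| 0.8 | 1.5–2.4 | 60% |
| ≥1.0 | 1.5–3.0 | 100% |

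**5. Which baselines can enter.** Inclusion criterion 8 caps b at 1.5 and requires Cockcroft-Gault clearance of at least 60 mL/min. For a man, the highest admissible creatinine is weight × (140 − age)/(72 × 60) mg/dL. The documents give no ULN in mg/dL, so 1.0 to 1.3 is assumed here.

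- 60 kg, age 70: 60 × 70/4320 = 0.972 mg/dL, so b ≤ 0.75 (ULN 1.3), 0.81 (1.2) or 0.97 (1.0). Share at most 50%, 62% or 94%.
- 70 kg, age 60: 70 × 80/4320 = 1.296 mg/dL, so b ≤ 1.00, 1.08 or 1.30. Share at most 99%, 100% or 100%.

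**6. Frequency.** Protocol Table 8 lists no related renal event of Grade 2 or higher among 5 + 6 = 11 DLT-evaluable combination patients, which is too few to give a rate. Section 2.3.2 names acute kidney injury among the serious reactions seen in at least 2% on nivolumab alone in colorectal cancer. So the row may well be used, but that figure is not a rate for this band.

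**The case against.** The strongest reply is that a coherent reading exists. Table 19 is introduced as a summary of the nivolumab prescribing information, and the added line pairs naturally with the entry above 6x ULN: hold up to 6x, stop beyond it. On that reading it is a hold threshold spanning Grades 2 and 3, left beside grade-based management text. Both rows do withhold by default, under the same restart footnote. But the protocol does not state this reading, and it would still clash with the Grade 2 clause that lets nivolumab continue when the cause is not immune-related.

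A second reply is that the line may not belong to the Grade 3 action at all. In the text version of this table two labels do land in the wrong cell (Grade 3 hepatitis and Guillain-Barré syndrome), but both follow directly on a page break. The Grade 3 nephritis entry starts its own row with its label in the severity column. If the line were a separate row, it would still overlap Grade 2.

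Third, an investigator who grades by label first would reach the Grade 2 row, and the Grade 2 row does not forbid admission. On monitoring, following the stricter row satisfies both. These points stand: on admission and monitoring the likely error is extra caution. They do not settle which row governs.

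Finally, the percentages are shares of a creatinine band, not of patients, and step 5 works only two hypothetical men. That is correct and limits what they show.

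**Conclusion.** The concern holds as stated. The Grade 3 nephritis cell contains a range that contradicts its own label and covers all of the Grade 2 ULN band, with different instructions attached to the two rows.

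The reach is small. The nivolumab instructions differ at first occurrence only when the rise is not attributed to an immune-related event. Patients with baseline at or below 0.5x ULN are unaffected. Reported adverse event grades follow CTCAE v5.0 (Sections 6.6 and 9.4.3.1), and neither disease control rate in Arm A nor objective response rate in Arm B is touched. Few patients are likely to be involved, and no event rate can be given.

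The overlap itself rests on no assumption. The entry-limit figures in step 5 rest on the assumed ULN of 1.0 to 1.3 mg/dL. The correction should be made because it resolves contradictory safety instructions at almost no cost.

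**What to change.** Delete the added line ("Serum creatinine more than 1.5 and up to 6 times the ULN") from the Grade 3 cell and change nothing else. The ULN bands then read: Grade 1 above 1 to 1.5x, Grade 2 above 1.5 to 3x, Grade 3 above 3 to 6x, and permanent discontinuation above 6x. There is no gap and no overlap, and 2x ULN falls in Grade 2 alone on the ULN scale. CTCAE v5.0 remains the default grading for Table 14.

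The cost is one line in one table, by amendment or clarification letter. No procedure is added, and investigators can still admit a Grade 2 patient on clinical grounds.
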